5.1.2 Expansion Phase

Once the MTD is established, an additional cohort of patients will initially be treated with pazopanib alone, and tumor biopsies will be obtained to assess target inhibition, as outlined below. Tumor biopsies will be mandatory during the expansion phase of the study. Biopsies will be obtained at the time points outlined below. Depending on the results obtained from the tumor biopsies in the first few patients, the timing of the biopsy can be adjusted, but the number of tumor biopsies and the procedure will not change. Any change in the timing of the tumor biopsy will be discussed with the patient prior to obtaining informed consent.

The cohort and dosing regimens after establishment of the MTD are described below. When administered as a single agent during the expansion phase, the dose of pazopanib will correspond to the dose determined for the combination MTD if the MTD is determined at dose level 5 (ARQ 197 360 mg BID/pazopanib 800 mg QD) or 6 (ARQ 197 360 mg BID/pazopanib 600 mg QD). Otherwise, the dose of pazopanib will be determined after discussion with CTEP. Once the MTD is established, the data will be discussed with CTEP prior to proceeding with accrual for the expansion phase.

Cohort A (12 patients): Pazopanib will be given once daily as single agent from cycle 1 day 1 to day 7. Tumor biopsy will be done before drug administration on study (baseline) and on cycle 1 day 8, 8-12 hours after pazopanib administration. **After** the tumor biopsy, patients will start to receive ARQ 197 in addition to pazopanib at the combination MTD.

Twelve evaluable patients with both pre- and post-treatment biopsies will be treated initially in Cohort A. Mean increases in MET and pMET in these 12 patients will be measured to assess whether or not they are statistically significant.

For the purposes of final analysis of the expansion phase, only patients with paired tumor biopsies will be considered evaluable. Patients with fewer than the 2 required biopsies will not be considered evaluable for the expansion phase and will need to be replaced in the accrual scheme of the expansion phase. If a patient has a dose-limiting toxicity (DLT) with the single lead-in agent pazopanib in the expansion cohort, the patient will be taken off treatment.

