5.2.1 Grade \geq 3 Non-Hematological Toxicity

Grade \geq 3 non-hematological toxicity felt to be related to study medications will be considered dose-limiting with the following clarifications:

- 5.2.1.1 Diarrhea Grade 3 will only be considered dose-limiting if it is refractory to treatment as outlined in [Section 5.3.2](#), Supportive Care Guidelines, and unable to be corrected to Grade 2 or less within 24 hours. Bloody or Grade 4 diarrhea will be dose-limiting.
- 5.2.1.2 Nausea and vomiting Grade 3 will only be considered dose-limiting if it is refractory to anti-emetic therapy and unable to be corrected to Grade 1 or less within 24 hours ([Section 5.3.1](#)).
- 5.2.1.3 Rise in creatinine to Grade 3, not corrected to Grade 1 or less within 48 hours with IV fluids will be considered dose-limiting. All Grade 4 rises in creatinine will be dose limiting.

5.2.1.4 Grade ≥ 3 metabolic toxicities unable to be corrected to Grade 2 or less within 48 hours (such as glucose changes, hypocalcemia or hypercalcemia, hypomagnesemia or hypermagnesemia, hyperuricemia, hypophosphatemia, and hyponatremia) will be considered dose limiting. For hypokalemia or hyperkalemia, grade ≥ 2 toxicities unable to be corrected to grade 1 or less within 48 hours will be considered dose limiting. Grade 4 metabolic toxicities that are symptomatic will be considered dose-limiting regardless of duration or ability to correct.

5.2.1.5 QTc prolongation to ≥ 500 msec on at least two separate EKGs (refer to [Section 5.3](#)) will be dose limiting.

5.2.1.6 AST/ALT > 8 X ULN or AST/ALT > 3 X ULN and concurrent bilirubin elevation > 2 X ULN will be dose limiting.

5.2.1.7 Grade ≥ 3 bleeding in any sites or grade ≥ 2 pulmonary bleeding will be dose limiting.

5.2.1.8 Grade 4 venous thrombosis, pulmonary embolism, or any grade of arterial thrombosis will be dose limiting.

5.2.2 Grade 4 thrombocytopenia.

5.2.3 Grade 4 neutropenia ≥ 3 days or febrile neutropenia.

5.2.4 Any degree of anemia, leucopenia in the absence of grade 4 neutropenia ≥ 3 days, or lymphopenia will not be considered dose limiting.

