6 DOSING DELAYS/DOSE MODIFICATIONS

Toxicities (hematologic and non-hematologic; except any grade lymphopenia, anemia, or alopecia) should have resolved to \leq Grade 2 prior to starting the next cycle or receiving the next dose of pazopanib or ARQ 197 within a cycle. Study drugs should be held for hypokalemia or hyperkalemia \geq grade 2; hypocalcemia or hypercalcemia \geq grade 3; hypophosphatemia \geq grade 3; hypomagnesemia or hypermagnesemia \geq grade 3. These laboratory values should be corrected as soon as possible in a manner consistent with good medical judgment. Study drugs may be re-administered when hypokalemia or hyperkalemia is grade 1 or within institutional limits; hypocalcemia or hypercalcemia is \leq grade 2; hypophosphatemia is \leq grade 2; and hypomagnesemia or hypermagnesemia is \leq grade 2. Even though study drug administration is allowed at these lower grades, every effort should be made to correct the abnormal lab values to normal if possible. If the potassium level is grade 2 or greater and/or if the calcium, magnesium, and/or phosphate are grade 3 or higher, an EKG must be performed and appropriate action taken based on the results.

Treatment may be delayed for a maximum of 2 weeks for toxicities. In case toxicities do not resolve as stated, the patient will not receive further therapy on this protocol and will be followed for resolution of toxicities. Start of next cycle may be delayed for up to 1 week to accommodate scheduling conflicts. Dose modifications are intended for within-cycle and start-of-next-cycle changes. If administration of study drug is interrupted for any reason, it will not be made up, and

counting of the cycle days continues (i.e., if a patient stops pazopanib and ARQ 197 on day 15 and resumes 2 days later, they will be considered day 17).

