6.1 Dose Reduction

6.1.1 Doses will be modified for grade 3 or greater non-hematologic toxicity with the following clarifications:

- Doses will not be modified for electrolyte abnormalities, unless these are not correctable within 48 hours, or for alopecia.
- Dose of study drugs will not be reduced for nausea, vomiting, or diarrhea unless these are considered refractory as defined in [Section 5.3](#).
- Dose reductions may occur to a single compound, independent of the other compound. Doses of ARQ 197 will not be reduced for any grade hypertension or proteinuria.
- For uncontrolled hypertension (as defined in [Section 6.1.5](#)), only the dose of pazopanib will be reduced to the next lower dose level.
- For proteinuria, only the dose of pazopanib will be reduced to the next lower dose level ([Section 6.1.6](#)).

6.1.2 Grade 2 drug-related toxicity: No changes will be made to the dose of either study drug for Grade 2 toxicities, and therapy will not be interrupted, except as otherwise noted (e.g., hypokalemia or hyperkalemia as described above, Grade 2 hemorrhage or thrombosis as described in [Section 6.1.10](#)). However, for persistent symptomatic skin rash or hand foot syndrome limiting instrumental activities of daily living that do not improve to grade 1 or less within 2 weeks with optimal management, doses of both pazopanib and ARQ 197 will be held until toxicities have resolved to \leq Grade 1 prior to re-starting study treatment. Therapy will be re-initiated at the next lower dose level.

6.1.3 Grade 3 drug-related neutropenia and/or thrombocytopenia: Doses of both pazopanib and ARQ 197 will be held until toxicities have resolved to \leq Grade 2 prior to re-starting study treatment. Therapy will be re-initiated at the same dose level at the first occurrence of either event. In the case of second occurrence of

either event, therapy will be re-initiated at the next lower dose level. Therapy will not be interrupted or doses modified for any grade lymphopenia, anemia, or leucopenia in the absence of grade 3 or 4 neutropenia.

6.1.4 Grade 4 drug-related neutropenia ≥ 3 days and/or thrombocytopenia: Doses of both pazopanib and ARQ 197 will be held until toxicities have resolved to \leq Grade 2 prior to re-starting study treatment. Therapy will be re-initiated at the next lower dose level.

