6.1.8 Management of Subjects with Elevations in AST, ALT and/or Bilirubin

Table 7: Management of Liver Function Test Abnormality

AST, ALT and/or Bilirubin	
Isolated AST/ALT elevations between 3X ULN and 8X ULN	Continue pazopanib, but monitor weekly until AST/ALT returns to ≤ 2.5 or baseline
AST/ALT > 8 X ULN	Hold pazopanib until AST/ALT returns to ≤ 2.5 X ULN or baseline. If the potential benefit of reinitiating pazopanib treatment is considered to outweigh the risk for hepatotoxicity, then consider reintroducing pazopanib at a reduced dose of 400 mg once daily and measure serum liver tests weekly for 8 weeks only after discussion with the PI and CTEP. If AST/ALT elevations > 3 X ULN recur, then pazopanib should be permanently discontinued.
AST/ALT > 3 X ULN and concurrent bilirubin elevations > 2 X ULN	Permanently discontinue pazopanib.
Mild indirect hyperbilirubinemia, known or suspected Gilbert's syndrome, and elevation in ALT > 3 X ULN	Continue pazopanib, but monitor weekly until ALT returns to grade 1 (NCI CTCAE) or baseline.

6.1.9 Reversible Posterior Leukoencephalopathy Syndrome (RPLS) or similar leukoencephalopathy syndrome

RPLS or clinical syndromes related to vasogenic edema of the white matter have been rarely reported in association with pazopanib therapy ($< 3\%$). Clinical presentations are variable and may include altered mental status, seizure, and cortical visual deficit.

Hypertension is a common risk factor in patients who develop RPLS. MRI scans are key to diagnosis and typically demonstrate vasogenic edema (hyperintensity in T2 and FLAIR images and hypointensity in T1 images) predominantly in the white matter of the posterior parietal and occipital lobes; less frequently, the anterior distributions and the

gray matter may also be involved. RPLS should be in the differential diagnosis in patients presenting with unexplained mental status changes, visual disturbance, seizure or other CNS findings. RPLS is potentially reversible, but timely correction of the underlying causes, including control of blood pressure and interruption of the offending drug, is important in order to prevent progression to irreversible tissue damage. Pazopanib should be held in patients with symptoms/signs suggestive of RPLS, pending work-up and management, including control of blood pressure. Pazopanib should be discontinued upon diagnosis of RPLS.

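### Table 7 gives opposite pazopanib instructions, continue and hold, to a Gilbert's patient with ALT above 8 times ULN, and nothing says which row governs

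*Combined protocol and SAP*

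**What the plan says.** Table 7 (Section 6.1.8) has four rows. With AST, ALT and bilirubin in multiples of ULN:

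- **Continue row**: "Isolated AST/ALT elevations between 3X ULN and 8X ULN". Pazopanib continues with weekly monitoring. The range has both ends written out.
- **Hold row**: AST/ALT above 8. The action is "Hold pazopanib until AST/ALT returns to" at most 2.5 times ULN or baseline. If benefit is then judged to outweigh the hepatic risk, staff may "consider reintroducing pazopanib at a reduced dose of 400 mg once daily and measure serum liver tests weekly for 8 weeks only after discussion"; that discussion involves the PI and CTEP. Recurrence above 3 means permanent discontinuation. The condition is not restricted to isolated elevations and has no Gilbert's exception.
- **Stop row**: AST/ALT above 3 with simultaneous bilirubin above 2. Pazopanib is stopped permanently.
- **Gilbert's row**: known or suspected Gilbert's syndrome, mildly raised indirect bilirubin, ALT above 3. The action is "Continue pazopanib, but monitor weekly until ALT returns to grade 1 (NCI CTCAE) or baseline". Only the lower ALT bound is given, and mild has no number.

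Four other places bear on the same patient:

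- Section 5.2.1.6 makes drug-related AST/ALT above 8 dose-limiting. Its second limb (AST/ALT above 3 "and concurrent bilirubin elevation" above 2) matches the stop row. Neither limb mentions Gilbert's.
- Section 6 asks that toxicities settle to Grade 2 or lower "prior to starting the next cycle or receiving the next dose of pazopanib or ARQ 197 within a cycle".
- Section 6.1.1 opens with "Doses will be modified for grade 3 or greater non-hematologic toxicity with the following clarifications". The clarifications that follow do not mention liver tests or Gilbert's.
- Section 5.1.2 says that if a patient has a DLT "with the single lead-in agent pazopanib in the expansion cohort, the patient will be taken off treatment".

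**The concern.** The hold row and the Gilbert's row are both stated rules, and above 8 times ULN they tell staff to do opposite things for the same patient. The Gilbert's row is the more patient-specific of the two and comes last in the table, so it could fairly be taken as an exception to the hold row.

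Staff who took it that way would continue pazopanib through an event that Section 5.2.1.6 calls dose-limiting. They would also bypass everything attached to the hold row: the recovery threshold, the discussion with the PI and CTEP, the 400 mg restart dose, the eight weeks of weekly tests and the permanent stop on recurrence. Section 2.2 reports fatal hepatic failure with pazopanib (2 of 977 patients in the trials supporting the renal cell indication, 1 of 240 in the randomized soft tissue sarcoma trial), and Section 5 sets up liver monitoring because of it. The table that turns those tests into dosing decisions should give one answer.

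**Working it through.** The plan has no figure to reproduce here. The check compares the row conditions and then looks for a rule that ranks them.

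**1. Which rows are met.** Values are multiples of ULN. AST/ALT is taken to mean either enzyme. Because mild has no number, its upper bilirubin bound is assumed at 1.5, 2 or 3. AST is not above 8 unless shown. The last column applies the change set out in the fix.

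| Patient | Mild up to 1.5 | Mild up to 2 | Mild up to 3 | After the fix |
|---|---|---|---|---|
| Gilbert's, ALT 4, bilirubin 1.3 | Gilbert's | Gilbert's | Gilbert's | unchanged: continue |
| Gilbert's, ALT 7.9, bilirubin 1.3 | Gilbert's | Gilbert's | Gilbert's | unchanged: continue |
| Gilbert's, ALT 8.1, bilirubin 1.3 | hold + Gilbert's | hold + Gilbert's | hold + Gilbert's | hold |
| Gilbert's, ALT 10, bilirubin 1.3 | hold + Gilbert's | hold + Gilbert's | hold + Gilbert's | hold |
| Gilbert's, ALT 10, bilirubin 1.8 | hold | hold + Gilbert's | hold + Gilbert's | hold |
| Gilbert's, ALT 4, AST 9, bilirubin 1.3 | hold + Gilbert's | hold + Gilbert's | hold + Gilbert's | hold |
| Gilbert's, ALT 4, bilirubin 2.2 | stop | stop | stop + Gilbert's | unchanged: question for the sponsor |
| No Gilbert's, ALT 10, bilirubin 3 | hold + stop | hold + stop | hold + stop | stop |

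The conflict between hold and continue exists under all three assumed bounds. It is confined to AST or ALT above 8: from above 3 up to 8, the continue row and the Gilbert's row both say continue.

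The last three lines shape the fix. With ALT 4 and AST 9, a cap on ALT alone would leave both rows met, so AST must be covered too. With ALT 4 and bilirubin 2.2, the overlap is with the stop row and depends on what mild means. With ALT 10 and bilirubin 3, a blanket statement that the hold row governs above 8 would replace a permanent stop with a hold and a possible restart, so the precedence must be limited to the Gilbert's row.

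**2. Whether another rule settles it.**

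- Section 5.2.1.6 defines a DLT. It gives no dosing instruction for an individual patient and does not refer to Table 7.
- Sections 6 and 6.1.1 are general toxicity rules. They favour holding or modifying, since Section 5.2.1.6 sits under the Grade 3 or higher heading, but neither refers to Table 7 or Gilbert's.
- Nor do they carry the hold row's restart conditions. Section 6 defines one pazopanib step down as 800 to 600 mg or 600 to 400 mg. A patient on 800 mg who was held under the general rule could restart at 600 mg; the hold row specifies 400 mg.
- The off-treatment rule in Section 5.1.2 does settle the matter for a DLT on single-agent pazopanib, but only for days 1–7 of the expansion phase, which is week 1. Section 2.2 places ALT above 3 times ULN mainly in weeks 3 to 9, so the overlap is 0 of those 7 weeks. That timing is for ALT above 3, not above 8, and is not specific to Gilbert's patients.

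**3. Whether eligibility removes the case.** Section 3.1.9 allows bilirubin up to 1.5 and AST/ALT up to 2.5, but not both above ULN.

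- Bilirubin raised at entry: ALT is at most 1, so reaching the conflict needs a rise of more than 8 / 1 = 8-fold.
- Bilirubin normal at entry: ALT may be 2.5, so it needs a rise of more than 8 / 2.5 = 3.2-fold.

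Eligibility narrows the route to the conflict but does not close it. These ratios say nothing about how often it would occur.

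**The case against.** A sensible reading of the table exists. The first two rows divide the enzyme scale at 8. The last two deal with bilirubin: both start at 3 and neither has a cap. The Gilbert's row can then be read as the companion of the stop row, there to prevent a benign bilirubin rise from forcing a stop, with the hold row still applying to anything above 8. Sections 5.2.1.6, 6 and 6.1.1 point the same way, and a cautious clinician would probably hold. This stands as a good account of what may have been intended, and it keeps the severity low. It does not supply the missing rule, because no text states it and the competing reading, a specific row overriding a general one, is also reasonable.

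A second objection is that a remedy giving the hold row general priority above 8 would weaken the permanent stop for combined enzyme and bilirubin elevation. That is correct, and the fix is narrowed accordingly.

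Three stronger conclusions might be inferred, and the documents do not support them.

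- That the protocol directs staff to continue pazopanib above 8 times ULN. It does not: the hold row applies to the same patient, and the general rules lean toward it.
- That the Gilbert's row overrides permanent discontinuation. This cannot be established, because mild has no number and the two rows overlap only if it can exceed bilirubin 2 times ULN.
- That dose finding is affected. Section 5.2.1.6 counts a drug-related elevation above 8 as a DLT whichever row of Table 7 staff then follow.

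**Conclusion.** The point holds as a low-severity safety correction. For a patient with Gilbert's syndrome, AST or ALT above 8 times ULN (ALT above 3) and bilirubin mildly raised but not above 2, Table 7 gives two opposite instructions without ranking them. Harm would arise only if staff followed the less cautious one.

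The textual finding rests on taking AST/ALT to mean either enzyme only for the ALT 4, AST 9 case; the ALT cases do not need that assumption. It does not depend on which of the three bounds is assumed for mild. The number of patients affected is not stated. The case should be rare within the accrual ceiling of 56. No DLT count, MTD rule, endpoint or statistical figure changes.

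**What to change.** Amend Section 6.1.8, Table 7, in three respects:

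1. Limit the Gilbert's row to ALT above 3 and up to 8 times ULN, with AST also not above 8 times ULN.
2. State that the hold row (AST/ALT above 8 times ULN), with its restart conditions, takes precedence over the Gilbert's row only.
3. State that this does not alter the permanent-discontinuation row (AST/ALT above 3 with concurrent bilirubin above 2 times ULN), which takes priority over the hold row when both are met. The table does not rank those two rows either, so this sentence keeps the new precedence from being read as softening the permanent stop.

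Separately, ask the sponsor whether mild can exceed bilirubin 2 times ULN, and so whether the Gilbert's row is meant as an exception to permanent discontinuation. The text on that point should stay as it is until the sponsor answers.

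The cost is protocol wording. The downside is that a rare Gilbert's patient with AST or ALT above 8 times ULN, who might otherwise have continued, has pazopanib held.

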6.1.10 Management of Other Adverse Events

Adverse Event	Grade	Treatment Modification
Hemorrhage/ Bleeding	Grade 1	No interruption in treatment until hemoptysis. If hemoptysis, contact PI to determine if it is appropriate to continue pazopanib. Maintain current dose.
	Grade 2	For non-pulmonary bleeding, hold pazopanib unless resolved to \leq grade 1; reduce dose to next lower dose level, and continue treatment. For pulmonary bleeding, permanently discontinue pazopanib and remove subject from study. If grade 2 or greater hemorrhage/ bleeding recurs following dose reduction, stop pazopanib and remove subject from study.
	Grades 3 or 4	Discontinue treatment and withdraw subject from study.
Vascular/ Thrombosis	Grade 1	No interruption in treatment; maintain current dose.
	Grade 2, 3	Hold pazopanib until subject is receiving a stable dose of Low Molecular Weight Heparin (LMWH). Treatment may resume during the period of full-dose anticoagulation if all of the following criteria are met: 
 • The subject must have been treated with an anticoagulant at the desired level for at least one week. • The subject must not have had a grade 3 or 4 or significant grade 2 hemorrhagic event while on anticoagulant. Subject should be monitored as clinically indicated during anticoagulation treatment and after resuming study treatment. When treating with warfarin, international normalized ratio (INR) should be monitored within three to five days after any change in pazopanib dosing (e.g., re-initiating, escalating/de-escalating, or discontinuing pazopanib), and then at least weekly until the INR is stable. The dose of warfarin (or its derivatives) may need to be adjusted to maintain the desired level of anticoagulation.
	Grade 4 or pulmonary embolus	Discontinue treatment and remove subject from study.
Arterial Thrombosis/ ischemia	All grades	Discontinue pazopanib and remove subject from study.

7 ADVERSE EVENTS: LIST AND REPORTING REQUIREMENTS

Adverse event (AE) monitoring and reporting is a routine part of every clinical trial. The following lists of AEs (Section 7.1) and the characteristics of an observed AE (Section 7.2) will determine whether the event requires expedited reporting (via CTEP-AERS) **in addition** to routine reporting.

7.1 Comprehensive Adverse Events and Potential Risks Lists (CAEPRs)

7.1.1 CAEPR for Pazopanib (GW786034, NSC 737754)

The Comprehensive Adverse Events and Potential Risks list (CAEPR) provides a single list of reported and/or potential adverse events (AE) associated with an agent using a uniform presentation of events by body system. In addition to the comprehensive list, a subset, the Specific Protocol Exceptions to Expedited Reporting (SPEER), appears in a separate column and is identified with bold and italicized text. This subset of AEs (SPEER) is a list of events that are protocol specific exceptions to expedited reporting to NCI (except as noted below). Refer to the 'CTEP, NCI Guidelines: Adverse Event Reporting Requirements' http://ctep.cancer.gov/protocolDevelopment/electronic_applications/docs/aeguidelines.pdf for further clarification. *Frequency is provided based on 2383 patients.* Below is the CAEPR for Pazopanib (GW786034)

NOTE: Report AEs on the SPEER **ONLY IF** they exceed the grade noted in parentheses next to the AE in the SPEER. If this CAEPR is part of a combination protocol using multiple investigational agents and has an AE listed on different SPEERs, use the lower of the grades to determine if expedited reporting is required.

Version 2.6¹, January 21, 2015

Adverse Events with Possible Relationship to Pazopanib (GW786034) (CTCAE 4.0 Term) [n= 2383]			Specific Protocol Exceptions to Expedited Reporting (SPEER)
Likely (>20%)	Less Likely (<=20%)	Rare but Serious (<3%)	
BLOOD AND LYMPHATIC SYSTEM DISORDERS			
	Anemia		Anemia (Gr 3)
		Hemolytic uremic syndrome ²	
		Thrombotic thrombocytopenic purpura ²	
CARDIAC DISORDERS			
		Left ventricular systolic dysfunction	
		Myocardial infarction	
	Sinus bradycardia		
ENDOCRINE DISORDERS			
	Hypothyroidism		
GASTROINTESTINAL DISORDERS			
	Abdominal pain		Abdominal pain (Gr 3)

Adverse Events with Possible Relationship to Pazopanib (GW786034) (CTCAE 4.0 Term) [n= 2383]			Specific Protocol Exceptions to Expedited Reporting (SPEER)
Likely (>20%)	Less Likely (<=20%)	Rare but Serious (<3%)	
	Constipation		Constipation (Gr 2)
Diarrhea			Diarrhea (Gr 2)
	Dyspepsia		
		Gastrointestinal fistula ³	Gastrointestinal fistula³ (Gr 2)
		Gastrointestinal hemorrhage ⁴	
		Gastrointestinal perforation ⁵	Gastrointestinal perforation⁵ (Gr 2)
	Mucositis oral		
Nausea			Nausea (Gr 3)
Vomiting			Vomiting (Gr 2)
GENERAL DISORDERS AND ADMINISTRATION SITE CONDITIONS			
	Edema limbs		
Fatigue			Fatigue (Gr 3)
	Fever		
HEPATOBIILIARY DISORDERS			
		Hepatic failure	
INVESTIGATIONS			
	Activated partial thromboplastin time prolonged		
Alanine aminotransferase increased			Alanine aminotransferase increased (Gr 3)
	Alkaline phosphatase increased		Alkaline phosphatase increased (Gr 2)
Aspartate aminotransferase increased			Aspartate aminotransferase increased (Gr 3)
Blood bilirubin increased			Blood bilirubin increased (Gr 3)
	Creatinine increased		Creatinine increased (Gr 2)
		Electrocardiogram QT corrected interval prolonged	
Lymphocyte count decreased			Lymphocyte count decreased (Gr 3)
Neutrophil count decreased			Neutrophil count decreased (Gr 3)
Platelet count decreased			Platelet count decreased (Gr 4)
	Weight loss		Weight loss (Gr 2)
White blood cell decreased			White blood cell decreased (Gr 2)
METABOLISM AND NUTRITION DISORDERS			
Anorexia			Anorexia (Gr 2)
	Dehydration		Dehydration (Gr 2)
	Hypercalcemia		
Hyperglycemia			Hyperglycemia (Gr 2)
	Hyperkalemia		Hyperkalemia (Gr 2)
	Hypermagnesemia		
	Hypernatremia		
	Hypoalbuminemia		Hypoalbuminemia (Gr 2)
	Hypocalcemia		Hypocalcemia (Gr 2)
	Hypoglycemia		Hypoglycemia (Gr 2)
	Hypokalemia		
	Hypomagnesemia		
Hyponatremia			Hyponatremia (Gr 2)

Adverse Events with Possible Relationship to Pazopanib (GW786034) (CTCAE 4.0 Term) [n= 2383]			Specific Protocol Exceptions to Expedited Reporting (SPEER)
Likely (>20%)	Less Likely (<=20%)	Rare but Serious (<3%)	
	Hypophosphatemia		Hypophosphatemia (Gr 2)
MUSCULOSKELETAL AND CONNECTIVE TISSUE DISORDERS			
	Arthralgia		Arthralgia (Gr 2)
	Back pain		
	Myalgia		Myalgia (Gr 2)
	Pain in extremity		
NEOPLASMS BENIGN, MALIGNANT AND UNSPECIFIED (INCL CYSTS AND POLYPS)			
	Tumor pain		
NERVOUS SYSTEM DISORDERS			
	Dizziness		Dizziness (Gr 2)
	Dysgeusia		Dysgeusia (Gr 3)
	Headache		Headache (Gr 2)
		Reversible posterior leukoencephalopathy syndrome	
RENAL AND URINARY DISORDERS			
		Acute kidney injury	
	Proteinuria		Proteinuria (Gr 2)
		Urinary fistula	Urinary fistula (Gr 2)
REPRODUCTIVE SYSTEM AND BREAST DISORDERS			
		Female genital tract fistula	Female genital tract fistula (Gr 2)
		Uterine fistula	Uterine fistula (Gr 2)
		Vaginal fistula	Vaginal fistula (Gr 2)
RESPIRATORY, THORACIC AND MEDIASTINAL DISORDERS			
	Cough		
	Dyspnea		
	Respiratory hemorrhage ⁶		Respiratory hemorrhage⁶ (Gr 2)
		Respiratory, thoracic and mediastinal disorders – Other (interstitial lung disease) ⁷	
SKIN AND SUBCUTANEOUS TISSUE DISORDERS			
	Alopecia		Alopecia (Gr 2)
	Palmar-plantar erythrodysesthesia syndrome		
	Rash maculo-papular		Rash maculo-papular (Gr 2)
Skin and subcutaneous tissue disorders - Other (hair color change/hair depigmentation)			Skin and subcutaneous tissue disorders - Other (hair color change/hair depigmentation) (Gr 2)
	Skin hypopigmentation		Skin hypopigmentation (Gr 2)
VASCULAR DISORDERS			
Hypertension			Hypertension (Gr 3)
		Thromboembolic event ⁸	
		Vascular disorders - Other (arterial thromboembolic event) ⁸	

¹This table will be updated as the toxicity profile of the agent is revised. Updates will be distributed to all Principal Investigators at the time of revision. The current version can be obtained by contacting [REDACTED] Your name, the name of the investigator, the protocol and the agent should be included in the e-mail.

²Thrombotic microangiopathy (TMA) which includes both Hemolytic uremic syndrome (HUS) and Thrombotic thrombocytopenic purpura (TTP) has been reported in clinical trials of GW786034.

³Gastrointestinal fistula includes Anal fistula, Colonic fistula, Duodenal fistula, Enterovesical fistula, Esophageal fistula, Gastric fistula, Gastrointestinal fistula, Ileal fistula, Jejunal fistula, Oral cavity fistula, Pancreatic fistula, Rectal fistula, and Salivary gland fistula under the GASTROINTESTINAL DISORDERS SOC.

⁴Gastrointestinal hemorrhage includes Anal hemorrhage, Cecal hemorrhage, Colonic hemorrhage, Duodenal hemorrhage, Esophageal hemorrhage, Esophageal varices hemorrhage, Gastric hemorrhage, Hemorrhoidal hemorrhage, Ileal hemorrhage, Intra-abdominal hemorrhage, Jejunal hemorrhage, Lower gastrointestinal hemorrhage, Oral hemorrhage, Pancreatic hemorrhage, Rectal hemorrhage, Retroperitoneal hemorrhage, and Upper gastrointestinal hemorrhage under the GASTROINTESTINAL DISORDERS SOC.

⁵Gastrointestinal perforation includes Colonic perforation, Duodenal perforation, Esophageal perforation, Gastric perforation, Ileal perforation, Jejunal perforation, Rectal perforation, and Small intestinal perforation under the GASTROINTESTINAL DISORDERS SOC.

⁶Respiratory hemorrhage includes Bronchopulmonary hemorrhage, Epistaxis, Laryngeal hemorrhage, Mediastinal hemorrhage, Pharyngeal hemorrhage, and Pleural hemorrhage under the RESPIRATORY, THORACIC AND MEDIASTINAL DISORDERS SOC.

⁷Interstitial lung disease may include, Adult respiratory distress syndrome, Pneumonitis, Pulmonary fibrosis, Respiratory, thoracic and mediastinal disorders - Other (Acute respiratory distress syndrome), Respiratory, thoracic and mediastinal disorders - Other (Aveolitis), Respiratory, thoracic and mediastinal disorders - Other (Bronchiolitis obliterans), Respiratory, thoracic and mediastinal disorders - Other (Interstitial fibrosis), Respiratory, thoracic and mediastinal disorders - Other (Interstitial pneumonia), Respiratory, thoracic and mediastinal disorders - Other (Interstitial pneumonitis), Respiratory, thoracic and mediastinal disorders - Other (Organizing pneumonia), Respiratory, thoracic and mediastinal disorders - Other (Pulmonary infiltrates), Respiratory, thoracic and mediastinal disorders - Other (Toxic pneumonitis).

⁸These events can result in life-threatening pulmonary, cardiac, cerebral, and other complications.

⁹Infection includes all 75 sites of infection under the INFECTIONS AND INFESTATIONS SOC.

Adverse events also reported on Pazopanib (GW786034) trials but with the relationship to Pazopanib (GW786034) still undetermined:

BLOOD AND LYMPHATIC SYSTEM DISORDERS - Febrile neutropenia; Hemolysis
CARDIAC DISORDERS - Acute coronary syndrome; Atrial fibrillation; Cardiac disorders - Other (sinus arrest); Cardiac disorders - Other (supraventricular extrasystoles); Cardiac disorders - Other (Takotsubo [Broken Heart Syndrome]); Cardiac disorders - Other (Torsades de Pointes); Chest pain - cardiac; Pericardial effusion; Supraventricular tachycardia

ENDOCRINE DISORDERS - Adrenal insufficiency

EYE DISORDERS - Blurred vision; Dry eye; Eye disorders - Other (asthenopia); Eye disorders – Other (eye/retinal hemorrhage); Eye disorders - Other (foreign body sensation in eyes); Eye pain; Floaters; Glaucoma; Photophobia; Retinal tear

GASTROINTESTINAL DISORDERS - Abdominal distension; Dry mouth; Duodenal obstruction; Dysphagia; Esophagitis; Flatulence; Gastroesophageal reflux disease; Gastrointestinal disorders - Other (hyperactive bowel); Gastrointestinal disorders - Other (oropharyngeal pain); Gastrointestinal disorders - Other (pneumatosis intestinalis); Gastrointestinal pain; Oral pain; Pancreatitis; Periodontal disease; Proctitis; Small intestinal obstruction

GENERAL DISORDERS AND ADMINISTRATION SITE CONDITIONS - Chills; Edema face; Malaise; Non-cardiac chest pain; Pain

INFECTIONS AND INFESTATIONS - Infection⁹

INJURY, POISONING AND PROCEDURAL COMPLICATIONS - Bruising

INVESTIGATIONS - Cardiac troponin T increased; Cholesterol high; Ejection fraction decreased; GGT increased; INR increased; Investigations - Other (blood lactate dehydrogenase increased); Investigations - Other (blood TSH increased); Lipase increased; Serum amylase increased; Weight gain

METABOLISM AND NUTRITION DISORDERS - Hypertriglyceridemia

MUSCULOSKELETAL AND CONNECTIVE TISSUE DISORDERS - Bone pain; Chest wall pain; Generalized muscle weakness; Head soft tissue necrosis; Muscle weakness lower limb; Muscle weakness upper limb; Musculoskeletal and connective tissue disorder - Other (muscle spasms); Neck pain

NERVOUS SYSTEM DISORDERS - Extrapyrimal disorder; Intracranial hemorrhage; Ischemia cerebrovascular; Memory impairment; Paresthesia; Peripheral sensory neuropathy; Stroke; Syncope; Transient ischemic attacks

PSYCHIATRIC DISORDERS - Agitation; Anxiety; Confusion; Depression; Insomnia; Suicide attempt

RENAL AND URINARY DISORDERS - Hematuria; Urinary frequency

REPRODUCTIVE SYSTEM AND BREAST DISORDERS - Irregular menstruation; Reproductive system and breast disorders - Other (vaginal necrosis); Vaginal discharge; Vaginal hemorrhage

RESPIRATORY, THORACIC AND MEDIASTINAL DISORDERS - Laryngeal edema; Pharyngolaryngeal pain; Pleural effusion; Pleuritic pain; Pneumothorax; Postnasal drip; Sore throat; Voice alteration

SKIN AND SUBCUTANEOUS TISSUE DISORDERS - Dry skin; Hyperhidrosis; Pruritus; Purpura; Skin hyperpigmentation; Skin ulceration

VASCULAR DISORDERS - Flushing; Hot flashes; Hypotension; Vasculitis

Note: Pazopanib (GW786034) in combination with other agents could cause an exacerbation of any adverse event currently known to be caused by the other agent, or the combination may result in events never previously associated with either agent.

